**15.4.2 Secondary Endpoint analysis**

There are 7 secondary endpoints. Impedance data from the interventions in the development and validation datasets will be the same as for the primary performance endpoint.

1. The concordance between aggregated occlusion measurements (clot scale) done by CSGS, and the histopathology results of the clot retrieved during the EVT procedure, regarding red blood cell content in the occlusion.
  - To determine the histopathological results of the clot, the RBC composition (value between 0 and 1) will be averaged over the 3 analyzed slides provided by the Core Laboratory.
  - Significant correlation will be judged at the 0.05 significance level by the t-statistic of the relation between RBC content as output by the prediction model and the RBC content as quantified by the MSB-staining histological analysis.
2. The ability of CSGS detecting the proximal end of the occlusion (sensor-scale), as compared to the physician's labelling (tag 'PRE-CLOT' for no occlusion contact and tag 'CLOT' for occlusion contact). The concordance will be judged by the Area Under the Receiver Operator Characteristic curve on the validation dataset. Evaluation will include those interventions from the validation set where the 'PRE-CLOT' and 'CLOT' tagged measurements were acquired with

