### 11.2 SECONDARY ENDPOINTS

The Secondary Endpoints are:

1. The concordance between aggregated occlusion measurements (**clot scale**) done by CSGS, and the histopathology results of the clot retrieved during the EVT procedure, regarding **red blood cell content** in the occlusion.
2. The ability of CSGS detecting the **proximal end of the occlusion** (sensor-scale), as compared to the physician's labelling (tag 'PRE-CLOT' for no occlusion contact and tag 'CLOT' for occlusion contact).
3. **Procedural success** defined as the ability to navigate CSGS to the occlusion site and measure electrophysiological properties of the occlusion.
4. The ability to perform binary classification of individual electrophysiological parameter measurements (**local scale**) by distinguishing local regions with substantial platelet content (**platelet-positive**) from regions with negligible platelet content (**platelet-negative**) in the occlusion.
5. The concordance between aggregated occlusion measurements (**clot scale**) done by CSGS, and the histopathology results of the clot retrieved during the EVT procedure, regarding **platelet content** in the occlusion.
6. The ability to perform binary classification of individual electrophysiological parameter measurements (**local scale**) by distinguishing local regions with substantial fibrin content (**fibrin-positive**) from regions with negligible fibrin content (**fibrin-negative**) in the occlusion.

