**Clinical investigation plan - CLOT OUT**

- at most one missing or anomalous individual measurement (see identification of anomalous measurements in 15.6).
3. Procedural success defined as the ability to navigate CSGS to the occlusion and measure electrophysiological properties of the occlusion. Procedural success is achieved from the moment that at least 1 evaluable measurement is captured by the CSGS.
  4. The ability to perform binary classification of individual electrophysiological parameter measurements (local scale) by distinguishing local regions with substantial platelet content (platelet-positive) from regions with negligible platelet content (platelet-negative) in the occlusion.
    - The ability to perform binary classification will be evaluated by the performance metric Area Under the Receiver Operator Characteristic curve (AUC of ROC) computed from the platelet-content score predicted on the validation dataset. The same methodology will be used as for the primary performance endpoint.
  5. The concordance between aggregated occlusion measurements (clot scale) done by CSGS, and the histopathology results of the clot retrieved during the EVT procedure, regarding platelet content in the occlusion.
    - To determine the histopathological results of the clot, the platelet composition (value between 0 and 1) will be averaged over the 3 analyzed slides provided by the Core Laboratory.
    - Significant correlation will be judged at the 0.05 significance level by the t-statistic of the relation between platelet content as output by the prediction model and the platelet as quantified by the CD42b immunochemistry staining histological analysis.
  6. The ability to perform binary classification of individual electrophysiological parameter measurements (local scale) by distinguishing local regions with substantial fibrin content (fibrin-positive) from regions with negligible fibrin content (fibrin-negative) in the occlusion.
    - The ability to perform binary classification will be evaluated by the performance metric AUC of ROC computed from the fibrin-content score predicted on the validation dataset. The same methodology will be used as for the primary performance endpoint.
  7. The concordance between aggregated occlusion measurements (clot scale) done by CSGS, and the histopathology results of the clot retrieved during the EVT procedure, regarding fibrin content in the occlusion.

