    - To determine the histopathological results of the clot, the fibrin composition (value between 0 and 1) will be averaged over the 3 analyzed slides provided by the Core Laboratory.
    - Significant correlation will be judged at the 0.05 significance level by the t-statistic of the relation between fibrin content as output by the prediction model and the fibrin content as quantified by the MSB-staining histological analysis.

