## 2. Study objective

The objective of the study is to evaluate the safety and the possibility of Clotild® Smart Guidewire System (CSGS) to provide electrophysiological measurements. The electrophysiological measurements will be used to update CSGS's database and thus improve the prediction accuracy of the model in providing physicians with insights for mechanical thrombectomy.

The **primary objective** of the study is to evaluate the **safety** of using Clotild® Smart Guidewire System (CSGS) at the occlusion location during an EndoVascular Thrombectomy (EVT) procedure for the treatment of subjects with acute ischemic stroke eligible for EVT.

Safety will be evaluated by means of the amount of intracranial vessel perforations and/or dissections with the CSGS during the procedure.

The **secondary objective** of the study is to evaluate the **performance** of CSGS, defined here as the feasibility to measure electrophysiological properties of the occlusion in vivo during EVT procedures for the treatment of acute ischemic stroke.

Performance will be evaluated by the ability to correctly binary classify the clot as Red Blood Cell (RBC) positive or RBC negative, platelet positive or negative and fibrin positive or negative. Performance endpoints that focus on clot characterization are split in two categories: one category that demonstrates the ability of an automatic system to correctly identify the local composition of a clot

(local-scale), and the other category that reveals the extent of concordance between a number of local scale measurements made from the CSGS and the histological characterization by the Core Laboratory (Core Lab) of the full clot retrieved during the EVT procedure (clot scale).

The **tertiary objective** of the study is to explore possible relationships between CSGS measurements and intervention parameters such as first pass effect, number of passes to successfully retrieve the clot and other key parameters. Due to the nature of the tertiary objectives, not all centers may contribute to the data collection.

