#### **iv. Statistical significance level**

A significance level of 0.05 will be used.

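### The three clot-scale endpoints are called concordance with histology, but the only stated criterion is a significant correlation, which does not respond to bias or scale error

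*Protocol*

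**What the plan says.** Protocol 11.2 introduces the endpoints with the words "The concordance between aggregated occlusion measurements", and Protocol 15.4.2 repeats the definition: "The concordance between aggregated occlusion measurements (clot scale) done by CSGS, and the histopathology results of the clot retrieved during the EVT procedure". SAP section 2 describes the clot-scale group as "the other category that reveals the extent of concordance between a number of local scale measurements made from the CSGS" and the core laboratory's histology of the whole clot.

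The reference is quantitative. In Protocol 15.4.2, "the RBC composition (value between 0 and 1) will be averaged over the 3 analyzed slides provided by the Core Laboratory"; platelets and fibrin are handled in the same way.

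The criterion in Protocol 15.4.2, repeated in SAP 4.c, is a significance test for each component:

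- RBC: "Significant correlation will be judged at the 0.05 significance level by the t-statistic of the relation between RBC content"
- Platelets: "Significant correlation will be judged at the 0.05 significance level by the t-statistic of the relation between platelet content"
- Fibrin: "Significant correlation will be judged at the 0.05 significance level by the t-statistic of the relation between fibrin content"

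SAP 8.c.iv adds only "A significance level of 0.05 will be used". Neither document states the sidedness, the type of correlation coefficient, a target correlation or a power figure for these tests. SAP 8.c.i promises bootstrap confidence intervals and SAP 8.c.xiii promises descriptive statistics, both in general terms. Neither names a mean difference, limits of agreement, concordance coefficient or calibration measure.

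**The concern.** Concordance between two measurements of the same quantity means that the values are close. A correlation test asks only whether they move together along some straight line. A model that overstates RBC content by the same amount in every clot, or halves it in every clot, obtains the same t-statistic as a model without that error.

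The consequence matters because of where these endpoints sit. The ground truth for the primary performance endpoint is labelling by the sponsor's own experts (Protocol 15.4.1 and 15.7), made by inspecting the signal together with the clot histology (SAP 4.b). Among the primary performance and secondary endpoints, the clot-scale ones are those compared with an independent laboratory that is stated to be blinded to the CSGS results. If p < 0.05 is reported there as concordance, the study's best external evidence will claim more than was tested. If p > 0.05, a useful relation may be dismissed because the sample is small.

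**Working it through.** **Inputs from the documents.** Validation set N_V = 14; 3 acquisitions per intervention; 5.44 independent measurements per acquisition; 53% RBC-positive; AUC 0.85 with a 95% CI width of at most 0.1 (Protocol 15.5). The clot-scale analysis set is the validation patients with a retrieved clot (Protocol 15.2). Clots were obtained in 30 of the first 31 treated subjects (Protocol 15.6), which implies 14 × 30/31 = 13.5, so 13 to 14 clots.

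**Assumptions, not in the documents.** SD 0.20 for both prediction and histology; two-sided Pearson test; bivariate normal data for power.

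**1. The plan's own figure.** Hanley-McNeil with Q1 = A/(2−A) = 0.739 and Q2 = 2A²/(1+A) = 0.781. With 14 × 3 × 5.44 = 228.5 measurements split 53/47, the CI width is 0.0994; with 13 interventions it is 0.1032. N_V = 14 therefore reproduces. It is sized for the AUC only, not for the clot-scale correlations.

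**2. What counts as significant.** Critical |r| = t/√(t² + n − 2). At n = 14, t = 2.179 and |r| = 0.532. At n = 13, |r| = 0.553.

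**3. The test against bias.** For r = 0.8 and n = 14, t = 0.8 × √12 / √(1 − 0.64) = 4.62, p = 0.0006. A constant bias d does not enter this formula. It does enter Lin's coefficient:

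CCC = 2·r·s₁·s₂ / (s₁² + s₂² + d²) = 0.064 / (0.08 + d²)

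| Bias d | CCC | p of the planned test |
|---|---|---|
| 0 | 0.80 | 0.0006 |
| 0.05 | 0.78 | 0.0006 |
| 0.10 | 0.71 | 0.0006 |
| 0.20 | 0.53 | 0.0006 |
| 0.30 | 0.38 | 0.0006 |

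Scale error behaves in the same way. Assume histology with mean 0.45 and SD 0.20, a prediction at half that level (mean 0.225, SD 0.10) and a correlation of 0.9. Then CCC = 2 × 0.9 × 0.2 × 0.1 / (0.04 + 0.01 + 0.0506) = 0.36, yet the test is significant in 99.9% of simulated trials at n = 14.

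**4. How much a p-value says at this size.** The Fisher 95% CI for a just-significant r at n = 14 is tanh(atanh 0.532 ± 1.96/√11), about 0.00 to 0.83.

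Power at n = 14 by simulation:

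| True correlation | Two-sided | One-sided |
|---|---|---|
| 0.4 | 30% | 43% |
| 0.5 | 47% | 60% |
| 0.6 | 67% | 78% |
| 0.7 | 85% | 91% |

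The Fisher approximation at 0.5, two-sided, is 44.5%. On the same approximation, 80% power needs 30 clots for a true correlation of 0.5 and 14 for 0.7.

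**The case against.** Five points can be made for the plan.

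**Loose wording.** Endpoint 2 also speaks of concordance and judges it by AUC, which likewise ignores shift and scale. Protocol 15.1 announces correlation analyses openly. Part of the problem is therefore the label. This stands, and it is why renaming is one of the two remedies. It does not remove the mismatch while the word and the stated aim remain.

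**Scale of the output.** A 0-1 scale is stated only for histology. The clot-scale model output is called content, but its units and aggregation rule are not given, and at local scale the model produces a ranking score. If the clot-scale output is also an uncalibrated score, Lin's coefficient and limits of agreement have no meaning. This stands and makes the remedy conditional.

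**Low stakes.** No go/no-go rule rests on these endpoints in this single-arm, first-in-human study, and general provision is made for intervals and descriptive statistics. That limits the consequence. It does not supply an agreement measure.

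**Chosen example.** The SD and the biases are illustrative. A range is shown for that reason; at 5 points of bias the loss is slight.

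**Agreement measures are imprecise too.** With a true CCC of 0.5 and no bias, simulated estimates at n = 14 span about −0.02 to 0.79. This is correct, and is why they should be reported as estimates rather than as a new pass mark.

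Stronger readings are tempting but not supported. A reader might infer that a moderate true relation usually fails the test. That depends on sidedness and on the true correlation, neither of which is stated; at n = 14 a correlation of 0.6 passes 67% of the time two-sided, and 0.5 passes 60% one-sided. A reader might also take 8 clots as the sample, from the 60% availability still given in SAP section 7 (14 × 0.6 = 8.4), where the critical |r| is 0.71. With 30 of 31 clots obtained, that is unlikely. Lastly, a significant negative correlation would fit the literal wording if the test is two-sided, but it could not reasonably be reported as concordance.

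**Conclusion.** The point holds in a limited form. The endpoints claim agreement, the criterion tests association, and no other part of either document names an agreement measure. That conclusion follows from the formula and needs no assumption.

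The size of the possible error is illustrative. With SD 0.20 and r = 0.8, the same p of 0.0006 goes with a CCC anywhere from 0.78 (5-point bias) to 0.38 (30-point bias). Nothing in the documents shows that the device is biased; the plan simply would not reveal it.

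The statement on information at 13 to 14 clots rests on a two-sided Pearson test: a just-significant result is compatible with a correlation from about 0.00 to 0.83, and at a true correlation of 0.5 the outcome is close to a coin toss. This should be corrected, but it does not threaten the primary endpoints.

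**What to change.** Amend the SAP before database lock, for endpoints 1, 5 and 7:

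1. State the units of the clot-scale model output and how local measurements are aggregated into it.
2. Stop using p < 0.05 as the criterion for concordance. Report the correlation, naming the coefficient, with its 95% CI.
3. If the output is a content fraction on the 0-1 scale, add the mean difference with limits of agreement, and Lin's CCC or a calibration slope and intercept. Give each with a CI, as estimates without a pass mark.
4. If the output is an uncalibrated score, call the endpoint association and make no claim of concordance.

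The cost is SAP text and a few lines of code on data already being collected. Results may look less favourable than a p-value, and all estimates will be imprecise at about 14 clots. A matching change to the protocol would have to be notified to, or approved by, the ethics committees and regulatory authorities (Protocol 16.2). Making the change in the SAP alone is the lighter route.

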**Clinical investigation plan - CLOT OUT**

- at most one missing or anomalous individual measurement (see identification of anomalous measurements in 15.6).
3. Procedural success defined as the ability to navigate CSGS to the occlusion and measure electrophysiological properties of the occlusion. Procedural success is achieved from the moment that at least 1 evaluable measurement is captured by the CSGS.
  4. The ability to perform binary classification of individual electrophysiological parameter measurements (local scale) by distinguishing local regions with substantial platelet content (platelet-positive) from regions with negligible platelet content (platelet-negative) in the occlusion.
    - The ability to perform binary classification will be evaluated by the performance metric Area Under the Receiver Operator Characteristic curve (AUC of ROC) computed from the platelet-content score predicted on the validation dataset. The same methodology will be used as for the primary performance endpoint.
  5. The concordance between aggregated occlusion measurements (clot scale) done by CSGS, and the histopathology results of the clot retrieved during the EVT procedure, regarding platelet content in the occlusion.
    - To determine the histopathological results of the clot, the platelet composition (value between 0 and 1) will be averaged over the 3 analyzed slides provided by the Core Laboratory.
    - Significant correlation will be judged at the 0.05 significance level by the t-statistic of the relation between platelet content as output by the prediction model and the platelet as quantified by the CD42b immunochemistry staining histological analysis.
  6. The ability to perform binary classification of individual electrophysiological parameter measurements (local scale) by distinguishing local regions with substantial fibrin content (fibrin-positive) from regions with negligible fibrin content (fibrin-negative) in the occlusion.
    - The ability to perform binary classification will be evaluated by the performance metric AUC of ROC computed from the fibrin-content score predicted on the validation dataset. The same methodology will be used as for the primary performance endpoint.
  7. The concordance between aggregated occlusion measurements (clot scale) done by CSGS, and the histopathology results of the clot retrieved during the EVT procedure, regarding fibrin content in the occlusion.
    - To determine the histopathological results of the clot, the fibrin composition (value between 0 and 1) will be averaged over the 3 analyzed slides provided by the Core Laboratory.
    - Significant correlation will be judged at the 0.05 significance level by the t-statistic of the relation between fibrin content as output by the prediction model and the fibrin content as quantified by the MSB-staining histological analysis.

**15.4.3 Tertiary Endpoint analysis**

There are 6 tertiary endpoints. Impedance data from the interventions in the development and validation datasets will be the same as for the primary performance endpoint. These endpoints are

**Clinical investigation plan - CLOT OUT**

more exploratory by assessing the correlation between the CSGS measurements with intervention parameters such as:

1. The arterial wall detection for individual measurement, specifically the local detection of arterial wall vs. clot when clot-contact is ensured.
2. The ability of CSGS detecting the distal end of the occlusion.
3. The ability of CSGS predicting the number of thrombectomy passes.
4. The ability of CSGS predicting the first pass effect (patients in whom the clot was removed on the first pass with a TICl score of 2c or 3).
5. The ability of CSGS predicting the etiology of the clot.
6. The ability of CSGS predicting the type of device(s) with better chances to remove the clot.

**15.5 STUDY SAMPLE SIZE CALCULATIONS**

The sample size calculation is driven by the number of patients needed in the development and validation datasets. The size of the development dataset is justified by the minimal number needed to achieve a target prediction performance for the primary performance endpoint. The size of the validation dataset is justified by the minimal number needed to achieve a sufficiently precise estimate of the primary performance endpoint around the target performance, as computed by the width of the confidence interval.

The sample size calculation is thus split in two parts, one for the development set and one for the validation set.

**Development set size**

The development set size was fixed to obtain a reasonable performance concerning the primary performance endpoint, based on preliminary research performed by SENSOME on an ex-vivo dataset ([DND\\_tr-0033-clot-composition-phenomenological-model-development\\_v1](#)). The standard approach at Sensome was to use machine learning techniques to cope with the complexity of the signal. However, our accumulated experience guided the design of a phenomenological model (based on observations and on physical properties of the signal). Its performance on local-scale composition prediction, evaluated on the ex-vivo dataset, is comparable to the machine learning model performance previously developed. The fine-tuning of its parameters has got only a minor influence on the performance, as assessed on the ex-vivo dataset.

Its extrapolation for thrombectomy-like procedures requires an additional rule to distinguish the arterial wall and potentially a fine-tuning of one of its parameters. Overall the number of examples needed to complete the first local-scale clot composition prediction model is constrained by the observation of ideal cases (locally pure RBC content and locally pure platelets content). Based on the

**Clinical investigation plan - CLOT OUT**

fraction of pure cases that was observed on the ex-vivo data set, and on rules to sub-sample this data set regarding the number of clot contact measurements per intervention, we find that  $N = 11$  is an adequate estimate of the development sample size.

We thus require a number of  **$N_D = 11$  interventions** with at least 1 evaluable measurement to be included in the development set to reach near optimal performance with respect to primary performance endpoint assessment (Development Performance Population).

**Validation set size**

The minimum number of  **$N_V$  interventions** to be included in the validation dataset to estimate the performance  $\hat{A}$  with sufficient statistical confidence margin is determined, with  $\hat{A}$  the area under the ROC curve (AUC) of the prediction model obtained on the validation sample of the population.

The following assumptions are made:

- **Estimated average number of independent individual measurements from a single tagged acquisition with clot contact = 5.44** (based on the quality check of data collected in the first 9 procedural successes)
- **Estimated average number of tagged acquisitions with clot contact per intervention = 3** (based on the quality check of data collected in the first 9 procedural successes)
- **Estimated number of RBC-positive cases = 53%** (based on the quality check of data collected in the first 9 procedural successes)
- **Expected number of RBC-negative cases = 47%**
- **An AUC of 0.85 is assumed with a maximal width of 0.1 for the 95% confidence interval**

With these assumptions, using the Hanley and McNeil estimate (Hanley and McNeil 1982) for the confidence interval to reach an expected AUC of 0.85 and a maximal width of the 95% confidence interval of 0.1, a number of  **$N_V = 14$  interventions** with at least 1 evaluable measurement valid interventions are necessary for the validation set (Local-Scale Performance Population).

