8.1.1 Clotild® Smart Guidewire

The guidewire has a standard 0.014” (0.36 mm) diameter and 2 m length. As mentioned above, its mechanical design was widely inspired by existing state of the art commercial guidewires.

[figure not shown]

FIGURE 2 SCHEMATIC VIEW OF THE CLOTILD® SMART GUIDEWIRE'S CROSS-SECTION

The sensor is composed of 3 rows of electrodes with 3 electrodes per row, totalling 9 electrodes. An electrophysiological measurement is performed between a pair of two electrodes. Thus, the sensor can perform 3 measurements in between the 3 pairs of electrodes per row, so a total of 9 measurements for the entire sensor. These individual impedance measurements at the scale of a single electrode pair are defined as the ‘local scale’. The aggregation of the 9 individual measurements, consisting in a full acquisition by the sensor, is defined as the ‘sensor scale’. When several

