### Validation set size

The minimum number of  $N_V$  interventions to be included in the validation dataset to estimate the performance  $\hat{A}$  with sufficient statistical confidence margin is determined, with  $\hat{A}$  the area under the ROC curve (AUC) of the prediction model obtained on the validation sample of the population.

The following assumptions are made:

- **Estimated average number of independent individual measurements from a single tagged acquisition with clot contact = 5.44** (based on the quality check of data collected in the first 9 procedural successes)

- **Estimated average number of tagged acquisitions with clot contact per intervention = 3** (based on the quality check of data collected in the first 9 procedural successes)
- **Estimated number of RBC-positive cases = 53%** (based on the quality check of data collected in the first 9 procedural successes)
- **Expected number of RBC-negative cases = 47%**
- **An AUC of 0.85 is assumed with a maximal width of 0.1 for the 95% confidence interval**

With these assumptions, using the Hanley and McNeil estimate (Hanley and McNeil 1982) for the confidence interval to reach an expected AUC of 0.85 and a maximal width of the 95% confidence interval of 0.1, a number of  **$N_v = 14$  interventions** with at least 1 evaluable measurement valid interventions are necessary for the validation set (Local-Scale Performance Population).

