### **Validation dataset**

After completion of the development phase, data of the following interventions will be used in the validation dataset. The validation dataset shall be used to assess the generalization performance of the model(s) developed during the development phase. When moving to the validation stage, all steps used from input data, i.e. individual impedance spectrums for each electrode pair, to the score prediction shall be fully determined. When moving to the validation phase the model(s) shall be locked, remaining unchanged during the course of the validation phase.

This same procedure of splitting the dataset into two sets (development dataset and validation dataset) will be performed for the primary performance endpoint assessment as well as for the secondary and tertiary endpoint assessments.

Confidence intervals will be computed with the bootstrap.

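### The 0.1-wide confidence interval for the primary AUC is not assured, because 14 validation patients are sized as about 228 independent readings and the bootstrap unit is not named

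*Protocol*

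**What the plan says.** Protocol 15.5 and SAP section 6 give the same calculation for the validation set. They assume:

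- an "Estimated average number of independent individual measurements from a single tagged acquisition with clot contact = 5.44";
- an "Estimated average number of tagged acquisitions with clot contact per intervention = 3";
- 53% RBC-positive and 47% RBC-negative readings;
- an AUC of 0.85, with a 95% interval at most 0.1 wide.

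The first three rest on the first 9 procedural successes. N_V = 14 is then obtained "using the Hanley and McNeil estimate (Hanley and McNeil 1982) for the confidence interval to reach an expected AUC of 0.85". Interval width is the only reason given for the size of the validation set, and 14 feeds the total of 42.

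Protocol 8.1.1 describes three rows of three electrodes: "the sensor can perform 3 measurements in between the 3 pairs of electrodes per row", "so a total of 9 measurements for the entire sensor". Protocol 13.8 has one reference measurement and two to three measurements inside the occlusion of each patient. SAP 4.b says the experts label each reading from its signal and from the histology of the whole clot. The only dependence that section acknowledges is between the frequencies of one spectrum.

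On the analysis, SAP 8.c.i says only: "Confidence intervals will be computed with the bootstrap".

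**The concern.** The unit of analysis is the electrode-pair reading, but the sampled unit is the patient. The acquisitions of one intervention come from one clot, through one wire, against one reference measurement. Three pairs formed from three electrodes must also share electrodes. The Hanley-McNeil variance has no term for such dependence, and neither document gives an intraclass correlation (ICC), a design effect or a clustered variance.

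Two things are at stake. The precision that justifies the validation set may not be reached. And if the final interval also treats readings as independent, it will come out close to the planned 0.1 whatever the true uncertainty, and so appear to confirm the plan while covering less than 95%.

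**Working it through.** **1. Reproducing 14.** With A = 0.85:

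- Q1 = A/(2 − A) = 0.7391; Q2 = 2A²/(1 + A) = 0.7811; A² = 0.7225.
- Readings: 14 × 3 × 5.44 = 228.5, split 53/47 into 121.1 positive and 107.4 negative.
- SE² = [A(1 − A) + (n₊ − 1)(Q1 − A²) + (n₋ − 1)(Q2 − A²)]/(n₊n₋), so SE = 0.0254.
- Width = 2 × 1.96 × SE = 0.0994.

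Thirteen interventions give 0.1031. The smallest number of readings that meets 0.1 is 226, or 226/16.32 = 13.85 interventions, so 14. The total is (11 + 14)/0.60 = 41.7, so 42. The plan's figures are right on its own assumption, with 228.5 − 226 ≈ 2 readings to spare.

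**2. Relaxing independence.** Simulation of 14 patients with 16 readings each, AUC 0.85 and 53% positive. Normal patient effects act on the label and on the score. All ICCs are assumptions, because the documents give none. Where repeated runs differed slightly, the range is shown. Coverage is that of a Hanley-McNeil interval treating readings as independent.

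| Label ICC | Score ICC | True 95% width | Coverage |
|---|---|---|---|
| 0 | 0 | 0.098 | – |
| 0.3 / 0.6 / 0.9 | 0 | 0.102 / 0.099 / 0.103 | – |
| 0 | 0.1 | 0.099 | – |
| 0 | 0.3 | 0.111 | – |
| 0.1 | 0.1 | 0.105 | 94% |
| 0.1 | 0.3 | 0.117 | – |
| 0 | 0.5 | 0.129–0.132 | 83% |
| 0.3 | 0.3 | 0.135–0.138 | 83–84% |
| 0.5 | 0.5 | 0.19 | 67–68% |
| 0.9 (extreme) | 0.5 | 0.24 | 57% |

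Label clustering alone does almost nothing. The large losses come when scores and labels both cluster.

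**3. Interval methods.** A bootstrap resampling readings stayed 0.095 to 0.097 wide in every scenario tried. Its coverage was about 94% without clustering and 81% at 0.3/0.3 (300 runs, error 2 to 3 points). A percentile bootstrap resampling whole patients covered about 85% to 93%, because 14 clusters are few. A clustered-ROC variance (Obuchowski) on the logit scale, with t on (patients − 1) degrees of freedom, covered 92% to 96%.

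**4. If 5.44 of 9 already removes dependence within an acquisition.** Only the three acquisitions per patient then remain correlated. As an approximation, the effective number of readings is 228.5/(1 + 2 × ICC). At ICC 0.1 this is 190.4 readings and width 0.109; at ICC 0.5 it is 114.2 readings and width 0.141.

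**5. Secondary endpoint 2.** This endpoint compares PRE-CLOT with CLOT tags from the same intervention. With one of each per patient, the true width falls as score ICC rises: 0.28, 0.25 and 0.23 at ICC 0, 0.3 and 0.5. Ignoring the pairing there may make the interval too wide.

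**The case against.** The best defence is that the sum is correct and independence is an openly declared assumption. The 5.44 out of 9 may already discount dependence within an acquisition. Clots are described as mixed (Protocol 6.3), and the endpoint concerns local regions within an occlusion, so labels need not agree within a patient. The performance analysis is descriptive (Protocol 15.1), with no AUC success threshold, and the primary objective is safety (Protocol 10.1). With weak clustering the plan comes out essentially as stated.

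All of that stands, and it limits the point. It does not supply what is missing: even on the favourable reading of 5.44, nothing discounts the factor of 3 acquisitions, and there is almost no slack.

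Four stronger readings are tempting and not supported:

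- **That the 0.1 width will be missed.** This depends on correlations the documents do not report.
- **That the SAP prescribes a bootstrap of readings.** It leaves the unit open. The endpoint is defined on individual readings, so resampling them is a natural choice, but it is a risk and not a stated rule.
- **That each patient counts as about one observation, or that label ICC is near 0.9.** Composition nearly constant within a clot sits badly with the mixed clots described; 0.9 serves only as an extreme case.
- **That the usual design effect with 16.32 readings per patient applies directly.** At ICC 0.1 it gives a width of 0.159, but that formula is for a mean. The simulated AUC at 0.1/0.1 has width 0.105.

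**Conclusion.** The concern holds as a statement about assurance. N_V = 14 follows from full independence of about 228 readings from 14 patients, an assumption neither document supports or relaxes. Over assumed label and score ICCs from 0 to 0.5, the expected width runs from about 0.10 to about 0.19. The lower end applies if only labels cluster or clustering is weak; 0.14 corresponds to 0.3/0.3 and 0.19 to 0.5/0.5. At those last two settings, an interval that ignores clustering covers about 84% and 67%. These figures rest on a binormal model with equal cluster sizes and on assumed ICCs. The absence of a clustering term and of a bootstrap unit is plain from the text; the size of the loss is not known.

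**What to change.** 1. **Protocol 15.5 and SAP section 6.** Keep N. State how 5.44 of 9 readings was derived and whether it already allows for dependence within an acquisition. Describe 0.1 as the width under full independence, and give the expected width as a range over label and score ICCs (about 0.10 to 0.19). Inform the range from the development interventions, noting that ICCs from about 11 patients are imprecise.
2. **SAP 8.c.i.** Name the patient as the cluster for AUC intervals. Use the Obuchowski clustered-ROC variance on the logit scale with t on (patients − 1) degrees of freedom. A plain percentile bootstrap of patients should not be the only method with 14 clusters.
3. **Secondary endpoints.** Apply the same interval to endpoints 4 and 6. Use a patient-clustered variance for endpoint 2 as well, giving the within-patient pairing as the reason.

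The cost is wording and a few lines of code, settled before the validation data are analysed. The stated precision becomes less favourable. No extra patients are needed.
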